The four sites were selected because they are diverse in terms of racial and ethnic composition of low-income residents, cost of living, urbanicity, and the generosity of state safety net programs such as Temporary Assistance to Needy Families (TANF) and state Earned Income Tax Credits (EITC); see Appendix 2. Recruitment (and our three subsequent annual data collections) will be spread evenly over the course of 12 months to avoid possible impacts of seasonal variation and to keep interviewer workload manageable. The Survey Research Center (SRC) at the University of Michigan will enroll participants and conduct baseline and age 1 survey interviews, survey interviews and home observation assessments at age 2, and survey interviews in the lab at age 3. SRC is especially skilled in fielding national studies that replicate protocols across multiple sites with high fidelity and provide data for the ongoing monitoring of the quality of recruitment efforts and data integrity. Extra quality assurance of these elements, as well as all age-3 cognitive and EEG data collection, will be conducted by our research team. The research team will also collect administrative data to obtain ongoing measurement of earned income and public benefits, possibly including health and Medicaid records and child protective services involvement. Conditional on early-wave findings, we will seek additional funding for follow-up assessments and analyses beyond the children’s third birthdays, including obtaining additional administrative data such as school records for the target children and their siblings.

Intervention. The intervention in this project is a simple income manipulation in the form of cash gift payments to families, funded by philanthropy. Mothers in the treatment group will receive monthly cash gift payments of \$333 (\$4,000 per year) for the first 40 months of the child’s life, paid on the day of the month of the child’s birthday by automatic loading on an electronic debit card. To put the magnitude of the payments in context, the proposed annual income supplement of \$4,000 would increase income in the average poor family in our pilot study by about 20%. Monthly text messages will announce the payment to recipients. We propose to pay families for 40 months to ensure that the age-3 lab-based data collection occurs well before the end of our cash gift payments. In order to eliminate any payment-mode effect, the control group will receive a

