At the ages 6 and 8 in-person visits at universities we will administer validated, reliable and developmentally sensitive measures of language, executive functioning and socioemotional skills. We will also collect the same measure of resting EEG that we did at age 4 (see below).

The family process measures that we will gather are based on two theories of change—via investments and stress—that might change in response to receipt of the cash gifts. *Investment pathway*: Additional income enables parents to buy goods and services for their families and children that support cognitive development. These include higher quality housing, nutrition and non-parental child care; more cognitively stimulating home environments and learning opportunities outside of the home; and, by reducing or restructuring work hours, more parental time spent with children. *Stress pathway*: A second pathway is that additional income may reduce parents' own stress and improve their mental health. This may allow parents to devote more positive attention to their children, thus providing a more predictable family life, less conflicted relationships, and warmer and more responsive interactions.

Analysis Plan

Pre-registered Hypotheses. As detailed in the Baby's First Years clinicaltrials.gov's Study Record Versions, we originally preregistered hypotheses with clinicaltrials.gov within a month after recruitment began (May, 2018) and have preregistered updates prior to each data collection wave.

Overview of Hypothesis Testing. Our Phase 2 key aims are to evaluate the impacts of the high- versus low-cash gifts on validated, reliable, and developmentally-sensitive measures of reading and math achievement, self-regulation, and socioemotional functioning, as well as lower rates of special education and grade retention at child ages 6 and 8 – this is Aim 1 in our Phase 2 NICHD application. Aim 2 calls for measurement of developmentally-sensitive electroencephalographic-based measures of brain functioning at child ages 6 and 8. Aim 3 is focused on hypotheses and data related to family expenditures, neighborhood quality, parent stress and mental health, parenting practices, and children's time spent in nonparental care, all gathered at child ages 6 and 8.

Analysis Plan for Phase 2

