"Take-up" of the cash gifts is virtually universal, with fewer than six families never having used their debit cards by child age 3. We will adjust standard errors using robust variance estimation techniques (Cameron et al. 2008). We will estimate (1) without and then with baseline demographic child and family characteristics (X) to improve the precision of our estimates by accounting for residual variation. These baseline measures, all gathered prior to random assignment, have been checked for adequate variation and sufficient independence from other baseline measures. They include: dummy variables for three of the four sites; mother's age, completed schooling, household income, net worth, general health, mental health, race and Hispanic ethnicity, marital status, number of adults in the mother's household, number of other children born to the mother, whether the mother smoked or drank alcohol during pregnancy and whether the father is currently living with the mother; and child's sex, birth weight, gestational age at birth, birth order and interview/assessor ID. For child outcomes we also control for child's age in months at the time of the survey/assessment.

Analysis Plan for Phase 2

We will apply our regression estimation strategy to the assessment-based measures of cognitive, language, self-regulation, and socio-emotional functioning and EEG measures of brain activity gathered at ages 6 and 8. To investigate family process impacts, we will apply our estimation strategy to maternal and family measures gathered at child ages 6 and 8.

Attrition. The greatest threat to internal validity is bias from sample attrition overall, within site, and differential attrition rates by treatment status overall and within site. We will carefully track response rates by site, by treatment status across sites, and then treatment status within site. Response rates were very high for the ages 1-3 data collections and varied across measures at age 4. Of the original 1,000 recruited participants, we secured interviews with 931 at age 1, 922 at age 2, and 922 again at age 3. By age 4, 5 mothers and 5 children had died and we gathered information on between $n=634$ (for child EEG) to $n=882$ (for maternal reports of behavior problems) of the remaining 990 families.

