- 1) We hypothesize slower pace of aging, as measured by DunedinPACE (Belsky et al., 2022), in the high-cash gift group, relative to the low-cash gift group. We will also report GrimAge Acceleration (Lu et al 2019; described above) and PhenoAge Acceleration as exploratory analyses. PhenoAge is conceptualized on the foundation of physiological markers and chronological age, which are subsequently employed to model a novel sample derived from DNA methylation, culminating in the establishment of a definitive DNA methylation clock (Levine et al., 2018). This metric exemplifies the age, measured in years, at which the average mortality risk in the NHANES III cohort aligns with the mortality risk as forecasted by the PhenoAge algorithm. PhenoAge will be based on principal components of DNA-methylation to bolster reliability (Higgins-Chen et al., 2022) and residualized for chronological age derived from sample receipt age to reflect accelerated biological age.

Changes to Control Variables Following the Posting of the Phase II Analysis Plan (finalized on July 3, 2025)

As with Age 4 analyses, for our Age 6 and 8 preregistered analyses, we have added controls for child age at the time of the data collection to adjust for age-related developmental differences that may affect both preregistered child and maternal outcomes. In the case of all preregistered outcomes gathered in lab assessments or maternal interviews, we will also control for an indicator for the interviewer/assessor for the specified outcome. In the case of non-survey and non-assessment measures (e.g. tract-level neighborhood poverty rate, school record test scores) we will adjust only for child age at the time of the interview.

These measures were not initially preregistered for analyses of child outcomes (Receptive One-Word Picture Vocabulary Test, Minnesota Executive Function Scale, Child Behavior Checklist, Resting Brain Activity, Matrices, Reading House, and Developmental Condition Diagnosis, age/sex adjusted BMI percentile and maternal report of child health) and maternal outcomes (depression, anxiety, and Body Mass Index (BMI)). Child age controls for age-related developmental differences that may affect both preregistered child and maternal outcomes, while the indicator for the interviewer/assessor has been added to account for any idiosyncratic assessor component to variation in preregistered child and maternal measures based on lab or survey assessments.

Analysis Plan for Phase 2

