Domains (in gray) and sub-domains	Measure source	Psychometrics	Age preregistered Primary Outcome	Age preregistered Secondary Outcome	Measures and notes (All measures between grey lines measured in the same wave will be subject to multiple testing adjustments)
Any Maternal Concern for Developmental Delay					
Parents' Evaluation of Developmental Status (PEDS)	Glascoe, 1997			3	Measured by the total score across categories of components of the PEDS, which includes 10 survey items.
Total "predictive concerns" in the PEDS	Glascoe, 1997			3	Measured by the total number of maternal-reported concerns that are "predictive of developmental delay" in the PEDS
School Achievement					
Retention	PSID, 2021			6, 8	Maternal report of whether the child has repeated a grade, adapted from the School Enrollment and Expectations section of the PSID Child Development Supplement. Item: Has child ever been held back a grade? (no/yes) Expect fewer retentions in high cash group.
School Behavior					
Suspensions	SIPP, 2023			6, 8	Maternal report of the number of school suspensions, adapted from the Survey of Income and Program Participation. Item: Has child ever been suspended or expelled from school? (no/yes) Expect fewer suspensions in high cash group.
Child engagement in school	Ehrle & Moore, 1999	Cronbach's alpha=.76		6, 8	Maternal report of child's engagement in school using an item adapted from the Survey of Income and Program Participation. "How often would you say that (CHILD) cares about doing well in school"? 4 answer choices: 1. none of the time; 2. some of the time, 3. most of the time; 4. all of the time. Score range: 1-4; higher scores indicate more engagement in school. Expect more engagement in high cash group.
Attendance	BFY PIs			8	During the last 12 months, how many times has (CHILD) been absent? Answer is estimated number of days. Expect fewer absences in high cash group.

Domains (in gray) and sub-domains	Measure source	Psychometrics	Age preregistered Primary Outcome	Age preregistered Secondary Outcome	Measures and notes (All measures between grey lines measured in the same wave will be subject to multiple testing adjustments)
School Quality					
School Quality	Stanford data matched to name of school and city/district			8	Gathered from school names and city/district. We expect an increase in school quality for the high cash group. The measure we select will be a function of what data will be available at the time of Age 8 wave.

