Notes. Previous versions of this table specified that "All measures between grey lines will be subject to multiple testing adjustments". This is now changed to be "All measures between grey lines measured *in the same wave* will be subject to multiple testing adjustments".

The previous version of this table referred to "waves" of data collection. For clarity, we have replaced "wave" with "age", with both referring to the age of the baby at planned data collection. Assessment target time is around the child's birthday for each wave, i.e. 12 months, 24 months, 36, months, 48 months, 72 months, and 96 months.

Minor, non-substantive changes may be made to the wording of specific items across data collection years.

Due to COVID-19, the age 3 data collection wave is in the form of a phone survey. Thus, sub-domains that were supposed to be measured in-person at ages 2 or age 3 were postponed to age 4. These domains include: epigenetic age, DNA methylation, BMI, physiological stress, self-regulation, executive function, social-emotional behavior, IQ; resting brain function, auditory discrimination brain function. The sub-domain of child vocalizations was not measured in-person at age 2 (due to COVID-19) and is not being measured at later ages, so it is removed from the pre-registration table.

*Indicates that the sub-domain was called something different in previous versions of this table. The changes are listed below:

- Previously "Communicative Development (Vocabulary)"; presently "Vocabulary".
- Previously "Intelligence"; then "IQ". Presently re-named to domain tested (not IQ per se)
- Previously "Language Related Brain Function"; presently "Auditory Discrimination Brain Function".

Language Development	
Language Milestones	Squires, J., Bricker, D. D., & Twombly, E. (2009). Ages & stages questionnaires . Baltimore, MD: Paul H. Brookes.
Language Processing	Golinkoff, R. M., De Villiers, J. G., Hirsh-Pasek, K., Iglesias, A., Wilson, M. S., Morini, G., & Brezack, N. (2017). User's Manual for the Quick Interactive Language Screener (QUILS): A Measure of Vocabulary, Syntax, and Language Acquisition Skills in Young Children . Paul H. Brookes Publishing Company

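### The age-6 models adjust for age at testing but not for expected time in school, leaving some removable variance in the achievement scores

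*SAP*

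**What the plan says.** Appendix Table 9 (Notes) fixes the visit calendar: "Assessment target time is around the child's birthday for each wave", which is 72 months for the age-6 wave. No visit window is given. The Protocol (Research Design) planned enrolment across a full year: "Recruitment (and our three subsequent annual data collections) will be spread evenly over the course of 12 months". All birth months should therefore occur in the sample.

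The Phase 2 SAP (Estimation strategy) includes baseline covariates for precision. The child-level items are "child's sex, birth weight, gestational age at birth, birth order and interview/assessor ID", followed by "For child outcomes we also control for child's age in months at the time of the survey/assessment". The addendum of July 3, 2025 states that "we have added controls for child age at the time of the data collection" and adds an assessor indicator. Neither place lists birth month, season, assessment date or school-entry cohort. School-entry cutoffs are not mentioned in either document.

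At age 6, Appendix Table 9 lists Applied Problems as primary (score range 0-56) and Letter-Word Identification as secondary (0-78), with no age or grade norming specified. Expressive vocabulary, also primary, is a sum of raw item scores. The retention item is registered at ages 6 and 8: "Has child ever been held back a grade? (no/yes) Expect fewer retentions in high cash group".

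**The concern.** With a single annual school-entry date, children tested on their sixth birthday range from almost no schooling to a full first school year, depending on the month of birth. Age at assessment is intended to absorb developmental differences, but the visit calendar holds it nearly fixed and lets school exposure vary. Age norming would not help either, because two children of the same age can differ by most of a school year.

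What is at stake is precision. The plan is powered at 80% for an effect of .18 SD one-tailed, so unexplained variance in a primary score matters somewhat, and the birth date behind it is already known for every child. The same calendar affects grade retention: a child who has not finished a grade can hardly have been made to repeat one, so an age-6 null would be weak evidence on that part of Aim 1.

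**Working it through.** **1. The plan's own figure.** Inputs from the Phase 2 SAP, Statistical power: n=800 split 320/480, 80% power, α=.05. MDE = (z₁₋α + z₀.₈)·√(1/320 + 1/480).
- One-tailed: (1.645 + 0.842) × 0.0722 = .179, against a stated .18.
- Two-tailed: (1.960 + 0.842) × 0.0722 = .202, against a stated .20.

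Both reproduce.

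**2. School exposure at exactly 72 months.** Assumptions, none in the documents: September 1 cutoff, 9.5-month school year, mid-month births spread evenly. Months in school for January to December births: 4.5, 5.5, 6.5, 7.5, 8.5, 9.5, 9.5, 9.5, 0.5, 1.5, 2.5, 3.5. The mean is 69/12 = 5.75. The variance is 513/12 − 5.75² = 9.69, so the SD is 3.11 months.

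**3. Variance explained and gain.** With β the assumed gain in SD per school year, R² = (3.11/9.5 × β)² and the SE ratio is √(1−R²). The net gain in children is 800 × [((770−k)/770)/(1−R²) − 1], where k is the degrees of freedom added and 770 residual degrees of freedom are assumed.

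| β | R² | SE reduction | Gross gain | One exposure term (k=1) | 11 month dummies | Birth quarter by site (k=12) |
|---|---|---|---|---|---|---|
| 0.4 | 1.7% | 0.9% | 14 | 13 | 2 | −6 |
| 0.7 | 5.3% | 2.7% | 44 | 43 | 32 | 8 |
| 1.0 | 10.7% | 5.5% | 96 | 95 | 83 | 31 |

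Calendar quarter does poorly because the assumed cutoff falls inside July to September. The quarter means are 5.5, 8.5, 6.5 and 2.5, with variance 151/4 − 5.75² = 4.69, and 4.69/9.69 = 48% of the exposure variance.

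**4. A second exposure model.** Taking exposure as uniform over 0 to 1 school year gives R² = β²/12. The one-tailed MDE falls from .1794 to .1789 (β=0.25), .1775 (0.5) or .1718 (1.0), equivalent to 0.5%, 2.1% or 9.1% more children. The order of size agrees with step 3, and at β=0.25 the gain is negligible (0.5% of 800 is 4 children).

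**5. Does age at assessment stand in?** In simulation with assumed visit lags, age explained about 3%, 22% and 53% of exposure variance for lag parameters of 1, 3 and 6 months. At 6 months, adding exposure at the actual visit to a model already containing age still gave 2.0% (β=0.5) to 9.0% (β=1.0) in equivalent sample size, or 16 to 72 children per 800.

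**6. Different cutoffs by site.** If one site's cutoff differs (assumed), common month dummies gave −0.3% to 3.5% for β of 0.5 to 1.0. Site-specific exposure gave 2.2% to 10.1%.

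**7. Retention.** On the step 2 calendar, June, July and August births have finished a school year at 72 months: 3/12 = 25%. With lag parameters of 1 to 6 months the share past a first school year is about 27% to 58%.

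**The case against.** The strongest reply is that this is an optional precision gain. Birth month is fixed before randomisation and balanced between arms in expectation, so the estimate, test and error rate are valid without it, and almost any trial could name one more useful covariate. That stands. A reader might infer that the treatment effect is confounded by schooling; nothing in the documents supports that.

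The size is also assumed. No section gives a cutoff, a school-year length or a gain per school year, and for month dummies the degrees of freedom consume the gain at the low end. That stands too, and it is why the form of the covariate matters.

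Third, age may vary more than the target suggests. Table 9 says around the birthday. Recruitment began about May 2018 and age-4 fieldwork started on July 9, 2022, so the earliest children were seen roughly two months late. It would be too strong to say that age adjustment captures nothing. It captures part, and step 5 shows that a useful remainder survives long lags. A term built on the target date cannot do better than exposure at the actual visit, so the gains in step 3 apply to visits near 72 months.

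Fourth, two extensions are tempting and unsupported. One is to prescribe the term for every child outcome at ages 6 and 8. No gain has been shown for age 8, or for EEG, nail cortisol, methylation or BMI. The other is to say that the Protocol's seasonal spreading has failed at age 6. That sentence covers recruitment and the three annual collections planned at the time, not the later waves.

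Finally, retention is already registered at age 8, so an informative test exists. That limits the retention point to how the age-6 result is labelled and read.

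**Conclusion.** The point holds as a modest precision issue for the age-6 achievement and cognitive scores. The planned adjustment omits a source of variance that is largely set by birth date and only partly tracked by age at assessment. On the stated assumptions a single exposure term is worth about 13, 43 or 95 children at n=800 for gains of 0.4, 0.7 or 1.0 SD per school year, and almost nothing at 0.25 SD. The result depends on a single annual entry date, births spread over the year and visits reasonably close to 72 months.

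Retention is a secondary limit on interpretation. A reader might infer that the age-6 test must be null. The documents do not establish that, because the 25% to 58% range rests on the same assumed calendar. They do leave a real possibility that many children will not have finished a grade by the visit.

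**What to change.** For the age-6 achievement and cognitive scores, add one pre-specified covariate to X: expected months of school exposure, computed from birth date, the 72-month target and the entry cutoff at the recruitment site. Keep age at assessment. Do not use actual grade, which is determined after randomisation and is affected by retention, itself an outcome. Do not use calendar birth quarter. The unadjusted model that the SAP already plans stays as it is.

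Report age-6 retention descriptively, with the share of children who have completed a grade, and rely on the registered age-8 test.

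The cost is one SAP sentence, a short table of site cutoffs and one degree of freedom, with no new data collection. The real drawback is another dated covariate change during fieldwork: an age-6 subtest was dropped on 9/17/2024, so that wave was already running, and the controls were last changed on July 3, 2025. If age-6 outcomes have already been examined by arm, present the adjusted result as a labelled sensitivity analysis.

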For ages 6 and 8 data collections, we will conduct sensitivity checks to evaluate whether missing data might be biasing estimates using weighting strategies and with multiple imputation. We will use two types of weights created by the Toolkit for Weighting and Analysis of Nonequivalent Groups (TWANG) (Ridgeway et al. 2022) in our regression analyses. Broadly speaking, TWANG uses generalized boosted models to flexibly estimate propensity scores and analytic weights. Generalized boosted modeling is a flexible and nonparametric estimation method that has been shown to outperform other algorithms for propensity score estimation with respect to bias (McCaffrey et al., 2004). These models will include all baseline control variables and the child's age.

First, we will create inverse probability of treatment weights, which are intended to provide estimates of the average treatment effect on the treated (ATT). In this approach, participants from the low-cash gift group analytic sample are weighted by the likelihood of being in the high-cash gift group analytic sample given their baseline observed characteristics, thereby creating a weighted sample in which the low-cash and high-cash gift groups have similar baseline characteristics. This should reduce any bias that is arising from non-equivalence on baseline covariates in the treatment and control analytic samples.

Second, we will create a set of non-response weights intended to adjust for missing data. These weights adjust regression estimates using a weight corresponding to the inverse probability of providing enough usable data to be included in our analytic sample. Weighting in this way produces an analysis sample with characteristics similar to the full BFY baseline sample.

We will also address the problem of missing data using multiple imputation strategies with all available data (including all survey and administrative data on outcomes and predictor variables). Multiple imputation is an appropriate method if, conditional on observed information, data are missing at random. Finally, because we have permission to collect administrative data from over 75% of mothers, we will be able to compare survey respondents and survey non-respondents on receipt of income from social programs.

Analysis Plan for Phase 2

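### The Phase 2 non-response model includes two predictors that unassessed families lack and does not name treatment arm, so its weights can collapse to a constant

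*SAP*

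**What the plan says.** The Phase 2 Analysis Plan, under Attrition, plans two kinds of TWANG weight: inverse-probability-of-treatment weights aimed at the ATT, and non-response weights equal to the inverse probability of being in the analytic sample. The second kind is meant to make the analysed families resemble the full baseline sample. One sentence sets the predictors for both: "These models will include all baseline control variables and the child's age".

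Under Estimation strategy the SAP lists the controls. It opens with "These baseline measures, all gathered prior to random assignment, have been checked for adequate variation", yet the list ends with "gestational age at birth, birth order and interview/assessor ID". It then adds: "For child outcomes we also control for child's age in months at the time of the survey/assessment". The July 2025 addendum to Phase 2 says of outcomes gathered in lab assessments or maternal interviews that "we will also control for an indicator for the interviewer/assessor for the specified outcome". The SAP's opening page describes the two added controls in the same way: age at assessment, and an indicator for the staff member who interviewed or assessed.

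Treatment arm is not named as a predictor of response. The same sections also plan response tracking by site, by arm and by arm within site; estimates with and without covariates; multiple imputation; and a comparison of respondents with non-respondents on administrative data.

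**The concern.** A response model has to be fitted on respondents and non-respondents together, so each predictor must have a value for both. Two of the named predictors come into being only when a family is assessed. A flexible model that sees them can predict response from the fact that they are missing, and then has no reason to use the true baseline variables. The weights stop varying, and the weighted result agrees with the unweighted one whatever the attrition did. A reader of the results would take that agreement as evidence of robustness.

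The omission of arm is a separate matter. The SAP ranks attrition, including differential loss by arm, as the main danger to validity. A single pooled model can restore the overall mix of families while leaving the two arms selected differently.

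The check carries some weight in Phase 2, because the Phase 2 attrition section does not repeat the worst-case bounds planned in Phase 1.

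**Working it through.** **1. Scale.** The SAP gives no figure for the weights. Its power figures supply a scale and reproduce with MDE = (z_α + z_0.80) × √(1/n_high + 1/n_low).
- n = 800 (320/480): the root is 0.0722, giving 0.179 one-tailed and 0.202 two-tailed (stated .18 and .20).
- n = 700 (280/420): the root is 0.0772, giving 0.192 and 0.216 (stated .19 and .22).

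**2. Who has each predictor.**

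| Predictor | Known for |
|---|---|
| Site, maternal, household and birth variables | families enrolled at baseline |
| Child's age, as defined in Estimation strategy and the addendum | families surveyed or assessed at that wave |
| Interviewer/assessor ID, as defined in the addendum | families surveyed or assessed at that wave |

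The treatment-weight model does not have this problem. It is fitted within the analytic samples, where both values exist.

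**3. The collapse.** Let R = 1 for respondents and w = 1/P(R = 1). The first tree split falls on whether age is missing, because that split is pure. Every family in the non-missing branch has R = 1, so the residuals there are identical and no baseline variable can improve the fit. All respondents share one fitted probability, which tends to 1, so w is constant and Σwy/Σw equals the plain mean.

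A simulation used boosted depth-2 trees, 1,000 families split 400/600, about 20% non-response and 60 replicates per scenario. Respondent weights lay between 1.00000005 and 1.00000007, and the weighted and unweighted estimates agreed to about 1e-16 in every replicate. With baseline variables only, the coefficient of variation of the weights was 0.13 to 0.21. If rows with missing predictors are dropped instead, every remaining family has R = 1 and no model can be fitted.

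**4. EEG.** At age 4, of 990 families, 634 had EEG and 882 had maternal reports.
- Without EEG: 990 − 634 = 356 (36%).
- Surveyed but without EEG: at least 882 − 634 = 248, and 248/356 = 70%.

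If age and interviewer come from the survey, they mark only the 990 − 882 = 108 families without maternal reports. The model can still use baseline variables to explain EEG loss among surveyed families, but it no longer corrects for who was not surveyed. If every EEG family was also surveyed, the average response probability behind the weights becomes 634/882 = 0.72 instead of 634/990 = 0.64.

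A small simulation under assumed response models (three replicates, about 880 surveyed and 570 with EEG) gave weight SDs of 0.26 to 0.36, against 0.35 to 0.49 with baseline variables only. The SD fell to 0.00 only when age was coded missing for everyone without EEG.

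**5. Arm.** These assumptions are not from the documents: true effect 0; four binary covariates, two shifting the outcome by 0.6 and 0.4 SD; response 0.84 in the high-cash arm regardless of covariates; response 0.77 ± 0.15 ± 0.075 in the low-cash arm according to the two prognostic covariates.

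Among low-cash respondents the covariate prevalences become 0.5 × 0.92/0.77 = 0.597 and 0.5 × 0.845/0.77 = 0.549. The expected bias is −(0.097 × 0.6 + 0.049 × 0.4) = −0.078 SD. Halving the assumed dependence gives −0.039; no dependence gives 0.

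| Unadjusted contrast | Mean estimate (SD) |
|---|---|
| Unweighted | −0.080 |
| Baseline + age at assessment | −0.080 |
| Baseline only, no arm | −0.081 |
| Baseline + arm, with interactions | −0.005 |
| Fitted separately by arm | −0.001 |
| Treatment (ATT) weights | 0.003 |

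The Monte Carlo standard error of the unweighted mean is about 0.010. Covariate-adjusted regression also gave 0.003. A two-sided 5% comparison of response rates flagged the difference in 80% of replicates (calculated power 78%).

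**6. Where the other checks do not substitute.** Now assume one response model in both arms (0.80 ± 0.15 ± 0.05) and an effect that varies by 0.4 SD across the first covariate but averages 0. The expected bias is (0.5 × 0.95/0.80 − 0.5) × 0.4 = 0.0375. Simulated: unweighted 0.036, with age at assessment 0.036, ATT weights 0.041, covariate-adjusted 0.042, baseline-only non-response weights −0.002, fitted by arm 0.000.

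**The case against.** Most of the listed predictors are true baseline variables. The TWANG sentence says only the child's age, and the wording "age in months at the time of the survey/assessment" belongs to the outcome regression. Age could mean the 72- or 96-month target in the table notes, the assessor could be the baseline interviewer, and missing values could be imputed. The SAP also says the weights should reproduce the baseline sample; constant weights would visibly fail that, and a careful analyst would notice.

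Part of this stands: the collapse depends on implementation and is only partial for outcomes missing among surveyed families. The innocent readings do not rescue the text. Target age is the same for every family at a wave and would add nothing. A baseline interviewer does not fit the addendum or the opening page. Imputing predictors for these models is not specified. A preregistered plan should not depend on the analyst departing from it.

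Three stronger readings are tempting and are not supported.
- A reader might infer that the whole attrition plan is blind to differential loss. Response tracking, treatment weights and covariate adjustment all reacted in the differential scenario, and multiple imputation is planned as well.
- A reader might infer that the SAP decided to leave arm out. It does not mention arm in the response model; it does not exclude it.
- A reader might set −0.08 SD beside the .18 SD detectable effect and infer that the trial's results are biased. That figure rests on assumed response rates and on the unadjusted contrast.

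Nor are the ATT weights an error. The main estimand remains intent-to-treat, and their different purpose is stated.

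**Conclusion.** The point holds for the Phase 2 non-response weights. Followed literally, the stated predictors make this check agree with the unweighted analysis by construction, or leave nothing to fit; for outcomes such as EEG they weaken it. The collapse needs no assumption about effect sizes, only that age and assessor are missing for non-respondents and that missingness is its own branch.

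The arm point is narrower. Pooled weights without arm do not correct arm-specific selection in the unadjusted contrast, and the other planned checks partly cover this. Removing the two respondent-only predictors was enough in the varying-effect scenario but not in the differential one, so both changes are needed. The documents give no basis for sizing any actual bias.

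No primary estimate, test or sample size changes. This should be corrected before the age-6 and age-8 sensitivity analyses, but it does not invalidate the main analysis.

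**What to change.** Amend the Phase 2 Attrition and Estimation strategy text as follows.

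1. Restrict the response model to variables known for all randomised families: pre-randomisation covariates and, where available, earlier-wave outcomes. A missing category for an earlier wave is acceptable, because it does not determine response at the current wave.
2. Remove assessor ID and age at assessment from the response model. They can stay in the outcome regressions.
3. Fit the response model separately by arm, or include arm and arm-by-covariate terms, and weight each arm to the full randomised sample so that the target stays the intent-to-treat effect.
4. Move assessor ID out of the list of measures said to predate random assignment.
5. Keep the ATT weights, if wanted, as a labelled sensitivity analysis.
6. Report the spread of the weights and baseline balance against all randomised families for each outcome, so that a collapse would be seen.

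The cost is a wording change and a different model call, with no new data. Weighted intervals will be somewhat wider because the weights now vary. Recruitment began around May 2018, so age-8 target dates start around 2026, after the July 2025 SAP; for that wave the change can be made in advance.
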